### 15.3.4. Immediate Reporting of Serious Adverse Events

In order to adhere to all applicable laws and regulations for reporting an SAE, the study site must formally notify [REDACTED] within 24 hours of the study site staff becoming aware of the SAE. It is the Investigator's responsibility to ensure that the SAE reporting information and procedures are used and followed appropriately.

#### Reporting Information for SAEs

Any SAE that occurs between the time that the subject has signed the ICF and the subject's final clinic visit (including FU Visit) must be reported to [REDACTED] within 24 hours of the study site staff becoming aware of the event. Thereafter, the event should be reported only if the Investigator considers it related to study treatment.

A report ***must be submitted*** to [REDACTED] regardless of the following:

- Whether or not the subject has undergone study-related procedures
- Whether or not the subject has received study treatment
- The severity of the event

CONFIDENTIAL

The information contained herein may not be used, disclosed, or published without the written consent of  
Biogen MA Inc.

- The relationship of the event to study treatment

To report initial or FU information on an SAE, fax or email a completed SAE form. Refer to the Study Reference Guide for country-specific [REDACTED] fax numbers or email [REDACTED]

#### 15.3.4.1. Deaths

Death is an outcome of an event. The event that resulted in death should be recorded on the appropriate CRF. All causes of death must be reported as SAEs within 24 hours of the site becoming aware of the event. The Investigator should make every effort to obtain and send death certificates and autopsy reports to [REDACTED]. The term death should be reported as an SAE only if the cause of death is not known and cannot be determined.

#### 15.3.5. Suspected Unexpected Serious Adverse Reactions

Suspected unexpected serious adverse reactions (SUSARs) are SAEs that are unexpected and judged by the Investigator or Biogen to be related to the study treatment administered.

Appropriate personnel in Biogen Safety and Benefit Risk (SABR) will unblind SUSARs for the purpose of regulatory reporting. Biogen or designee will submit SUSARs (in blinded or unblinded fashion) to regulatory agencies according to local law. Biogen or designee will submit SUSARs to Investigators in a blinded fashion.

### 15.4. Procedures for Handling Special Situations

#### 15.4.1. Pregnancy

**Subjects should not become pregnant or impregnate their partners during the study and for 24 weeks after their last dose of study treatment.** If a female subject becomes pregnant, study treatment must be discontinued *immediately*.

The Investigator must report a pregnancy occurring in a female subject by faxing the appropriate form to [REDACTED] within 24 hours of the study site staff becoming aware of the pregnancy at the SAE reporting fax number provided in the study reference manual. The Investigator or study site staff must report the outcome of the pregnancy to [REDACTED].

Congenital abnormalities and birth defects in the offspring of male or female subjects should be reported as an SAE if conception occurred during the study treatment period.

#### 15.4.2. Overdose

An overdose is any dose of study treatment given to a subject or taken by a subject that exceeds the dose described in the protocol. Overdoses are not considered AEs and should not be recorded as an AE on the CRF; however, all overdoses must be recorded on an Overdose form and faxed to [REDACTED] within 24 hours of the site becoming aware of the overdose. An overdose must be reported to [REDACTED] even if the overdose does

CONFIDENTIAL

The information contained herein may not be used, disclosed, or published without the written consent of Biogen MA Inc.

not result in an AE. If an overdose results in an AE, the AE must be recorded. If an overdose results in an SAE, both the SAE and Overdose forms must be completed and faxed to [REDACTED]. All study treatment-related dosing information must be recorded on the dosing CRF.

### 15.4.3. Medical Emergency

In a medical emergency requiring immediate attention, study site staff will apply appropriate medical intervention, according to current standards of care. The Investigator (or designee) should contact the [REDACTED] 24-hour emergency medical support number. Refer to the Study Reference Guide's Official Contact List for complete contact information.

#### 15.4.3.1. Unblinding for Medical Emergency

In this study, emergency decoding will be made available to the Investigator and designated personnel at Biogen through IRT.

In a medical emergency when knowledge of the subject's treatment assignment may possibly influence the subject's clinical care, the Investigator may access the subject's treatment assignment by IRT. However, prior to unblinding, the Investigator can contact the [REDACTED] 24-hour emergency medical support number at [REDACTED].

The Investigator must document the reasons for unblinding in the subject's source documents. The Investigator is strongly advised not to divulge the subject's treatment assignment to any individual not directly involved in managing the medical emergency, nor to personnel involved with the analysis and conduct of the study.

## 15.5. Contraception Requirements

For the purposes of this study, women of childbearing potential are defined as all women physiologically capable of becoming pregnant, UNLESS they meet one of the following conditions:

- Postmenopausal
  - 12 months of natural (spontaneous) amenorrhea without an alternative medical cause or 6 weeks after surgical bilateral oophorectomy with or without hysterectomy.
- Post hysterectomy.
- Female surgical sterilization (e.g., bilateral tubal ligation).

For the purposes of this study, highly effective contraception is defined as use of 1 of the following:

- For females of childbearing potential:
  - Established use of oral, injected, or implanted hormonal methods of contraception.
  - Placement of an intrauterine device or intrauterine system

CONFIDENTIAL

The information contained herein may not be used, disclosed, or published without the written consent of Biogen MA Inc.

- Barrier methods of contraception with use of a spermicide: condom or occlusive cap (diaphragm or cervical/vault caps) with spermicidal foam/gel/film/cream suppository. The use of barrier contraceptives should always be supplemented with the use of a spermicide.
- Male sexual partners underwent surgical sterilization with the appropriate postvasectomy documentation of the absence of sperm in the ejaculate.
- For males:
  - Vasectomy with negative semen analysis at FU.
  - Use of condoms with spermicide.
  - Female sexual partners who underwent surgical sterilization (e.g., bilateral tubal ligation), are postmenopausal, are post-hysterectomy, or are using highly effective contraception as listed above for female subjects.

For males and females of childbearing potential:

True abstinence, when this is consistent with the preferred and usual lifestyle of the subject, can be considered an acceptable method of contraception based on the evaluation of the Investigator who should also take into consideration the duration of the clinical trial. Periodic abstinence (e.g., calendar, ovulation, symptothermal, postovulation methods) and withdrawal are not considered acceptable methods of contraception.

Pregnancy reporting is described in Section 15.4.1.

## 15.6. Safety Responsibilities

### 15.6.1. The Investigator

The Investigator's responsibilities include the following:

- Monitor and record all AEs, including SAEs, regardless of the severity or relationship to study treatment.
- Determine the seriousness, relationship, and severity of each event.
- Determine the onset and resolution dates of each event.
- Monitor and record all pregnancies and FU on the outcome of the pregnancy in female subjects.
- Complete an SAE form for each SAE and fax it to Biogen (or designee) within 24 hours of the study site staff becoming aware of the event.
- Pursue SAE FU information actively and persistently. FU information must be reported to Biogen (or designee) within 24 hours of the study site staff becoming aware of new information.

CONFIDENTIAL

The information contained herein may not be used, disclosed, or published without the written consent of Biogen MA Inc.

- Ensure all AE and SAE reports are supported by documentation in the subjects' medical records.
- Pursue AE FU information, if possible, until the event has resolved or become stable.
- Report SAEs to local EC/IRBs, as required by local law.

#### 15.6.2. Biogen

Biogen's responsibilities include the following:

- Before study site activation and subject enrollment, the Clinical Monitor (██████) is responsible for reviewing with study site staff the definitions of AE and SAE, as well as the instructions for monitoring, recording, and reporting AEs and SAEs.
- Biogen (or designee) is to notify all appropriate regulatory authorities, central EC/IRBs, and Investigators of SAEs, as required by local law, within required time frames.

CONFIDENTIAL

The information contained herein may not be used, disclosed, or published without the written consent of Biogen MA Inc.

## **16. STATISTICAL METHODS AND DETERMINATION OF SAMPLE SIZE**

The objectives of the study and the endpoints to be analyzed are listed in Section 6.

### **16.1. Demography and Baseline Disease Characteristics**

Demographics and baseline data will be summarized by treatment group with summary statistics (mean, standard deviation [SD], median, and range) or with frequency distributions.

### **16.2. Efficacy and Pharmacodynamics**

#### **16.2.1. Analysis Population**

The intent-to-treat (ITT) population, defined as all subjects who were randomized and received at least 1 dose of study treatment (aducanumab or placebo), will be used for the efficacy analyses. Subjects will be analyzed in the groups to which they were randomized.

#### **16.2.2. Methods of Analysis**

##### **16.2.2.1. General Considerations**

Summary statistics will be presented. For continuous endpoints, summary statistics will generally include: number of subjects with data, mean, standard deviation, median, and range. For categorical endpoints, this will generally include: number of subjects randomized or dosed, number with data, and the percent of those with data in each category. Statistical testing for efficacy endpoints will be made between each aducanumab dose (high and low) and placebo. All statistical tests will be 2-sided.

##### **16.2.2.2. Aducanumab Doses to be Evaluated**

The following aducanumab doses as compared with placebo will be evaluated:

- Aducanumab high-dose (10 mg/kg in ApoE  $\epsilon$ 4 [including 6 mg/kg for subjects enrolled under protocol versions prior to Version 4 who do not have the opportunity to uptitrate to 10 mg/kg prior to completing Week 78 of the study] and 10 mg/kg in ApoE  $\epsilon$ 4 non-carriers).
- Aducanumab low-dose (3 mg/kg in ApoE  $\epsilon$ 4 carriers and 6 mg/kg in ApoE  $\epsilon$ 4 non-carriers).

In the event that the maximum dose (10 mg/kg) is terminated after the start of the study (Section 5.3.2) the definition of aducanumab high dose and aducanumab low dose will be modified as shown in Table 17. The dosing modification will be entirely based on interim analysis of outcomes that are independent of, and uninformative about, the treatment-related efficacy effect. Control of Type I error rate is thus maintained without a statistical adjustment for such adaptations [Chow and Chang 2011].

CONFIDENTIAL

The information contained herein may not be used, disclosed, or published without the written consent of Biogen MA Inc.

**Table 17: Treatment Groups in the Event of High Dose Group Termination**

High Dose Group(s) Terminated	Definitions of Revised Treatment (Low/High Dose) Groups for Comparison
ApoE ε4 carrier high-dose group (10 mg/kg) [including 6 mg/kg for subjects enrolled under versions prior to Version 4 who do not have the opportunity to uptitrate to 10 mg/kg prior to completing Week 78 of the study]	Low: ApoE ε4 carrier 3 mg/kg and non-carrier 6 mg/kg High: ApoE ε4 carrier 3 mg/kg and non-carrier 10 mg/kg
ApoE ε4 non-carrier high-dose group (10 mg/kg)	Low: ApoE ε4 carrier 3 mg/kg and non-carrier 6 mg/kg High: ApoE ε4 carrier 10 mg/kg and non-carrier 6 mg/kg
ApoE ε4 carrier high-dose group (10 mg/kg) AND ApoE ε4 non-carrier high-dose group (10 mg/kg)	ApoE ε4 carrier 3 mg/kg and non-carrier 6 mg/kg

### 16.2.2.3. Considerations for Multiple Comparison Adjustments

A sequential (closed) testing procedure will be used to control the overall Type I error rate due to multiple comparisons for the primary endpoint. The order of treatment comparisons is as follows: aducanumab high-dose versus placebo and aducanumab low-dose versus placebo. All comparisons after the initial comparison with  $p > 0.05$  will not be considered statistically significant.

Secondary endpoints have been rank prioritized, in the order shown in Section 6. In order to control for a Type I error for the secondary endpoints, a sequential closed testing procedure will be used and will include both the order of the secondary endpoints and treatment comparisons. Specifically, for each of the secondary endpoints, a sequential (closed) testing procedure, as for the primary endpoint, will be used to control the overall Type I error rate due to multiple treatment comparisons. If statistical significance is not achieved for 1 or 2 comparisons, all endpoint(s) of a lower rank will not be considered statistically significant for 1 or 2, respectively.

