### **16.8. Sample Size Considerations**

The study's sample size is based, in part, on results from a protocol-specified interim analysis from Study 221AD103, which included 1-year data from 1, 3, and 10 mg/kg treatment groups.

A sample size of 450 subjects per treatment group (1350 in total) was planned to have approximately 90% power to detect a true mean difference of 0.5 in change from baseline CDR-SB at Week 78 between the 2 treatment groups. This power calculation was based on a 2-sided t-test assuming equal variance with a final significance level of 0.05, an SD of 1.92, and a drop-out rate of 30%. The SD estimate of 1.92 for Week 78 reflected a 39% increase over the SD from the protocol-specified interim analysis of 1-year data.

The assumed true mean difference of 0.5 between the 2 treatment groups represents an approximately 25% reduction in the placebo mean change from baseline at Week 78 if the placebo mean change is estimated to be 2.

As defined in the prior versions of the protocol, the sample size for this study (and for the identically designed Study 221AD302) was reassessed in a blinded manner approximately 3 months before enrollment completion. At the time of this reassessment (November 2017), about 10.6% of the data was available on the primary endpoint from Study 221AD301 and Study 221AD302 combined; based on the pooled blinded data (i.e., treatment groups combined) from the 2 studies, the SD for the primary endpoint was estimated. As a result of this analysis, the sample size has been adjusted from 1350 to 1605 (450 to 535 per treatment) to assure adequate power to detect a mean treatment effect of 0.5.

CONFIDENTIAL

The information contained herein may not be used, disclosed, or published without the written consent of Biogen MA Inc.

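### Protocol Section 16.2.2.3 does not make the secondary endpoint sequence depend on the CDR-SB result, so high-dose MMSE is tested at two-sided 0.05 even if the primary endpoint fails

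*Protocol*

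**What the plan says.** Section 16.2.2.3 of protocol version 6.0 describes two procedures. The protocol versions reproduced before it use the same wording on this point.

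- Primary endpoint: "A sequential (closed) testing procedure will be used to control the overall Type I error rate due to multiple comparisons for the primary endpoint". Doses are taken in sequence, namely "aducanumab high-dose versus placebo and aducanumab low-dose versus placebo", and once a comparison exceeds 0.05 the later ones cannot be called significant.
- Secondary endpoints: "Secondary endpoints have been rank prioritized, in the order shown in Section 6". Section 6.2 lists them as MMSE, ADAS-Cog 13 and ADCS-ADL-MCI. For Type I error in this group, "a sequential closed testing procedure will be used and will include both the order of the secondary endpoints and treatment comparisons". Within each secondary endpoint the doses are tested in the same order as for the primary. The stopping rule is "If statistical significance is not achieved for 1 or 2 comparisons, all endpoint(s) of a lower rank will not be considered statistically significant", applied separately to the first and second dose comparisons.

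Section 16.2.2.1 adds "All statistical tests will be 2-sided". Sections 16.2.2.4 and 16.2.2.5, which give the primary and secondary analyses, contain no rule linking the two families. Neither do Sections 16.7 and 16.8.

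**The concern.** The ranks belong to the secondary endpoints, and the stopping rule works down those ranks. The first secondary test, high-dose MMSE, has nothing above it. It is carried out at 0.05 whatever happened to CDR-SB, so the primary and secondary families each spend a full two-sided 0.05.

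A trial that misses its primary endpoint could then report MMSE as significant under a procedure described as controlling Type I error. If MMSE succeeded, the two lower-ranked endpoints would be open as well. Whether a secondary result is confirmatory or descriptive after a failed primary should be settled by the rule itself. If it is left to be argued once CDR-SB is known, the answer is no longer prespecified.

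**Working it through.** **Inputs.** Two-sided testing is from Section 16.2.2.1, and the 0.05 threshold and dose order are from Section 16.2.2.3. Allocation is 1:1:1 (Section 9.2), so the two dose statistics on one endpoint correlate at 0.5 through the shared placebo arm. The correlation rho between the CDR-SB and MMSE statistics is not in the documents. It is assumed, with the range shown.

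**Step 1: reproduce the plan's own figure.** Section 16.8 says "A sample size of 450 subjects per treatment group (1350 in total) was planned to have approximately 90% power" for a difference of 0.5, "with a final significance level of 0.05, an SD of 1.92, and a drop-out rate of 30" per cent.
- Evaluable per arm: 450 × 0.70 = 315.
- Standard error: 1.92 × √(2/315) = 0.153.
- Standardised effect: 0.5 / 0.153 = 3.268.
- Power: Φ(3.268 − 1.960) = 0.905 (0.904 with the noncentral t).

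The stated 90% reproduces, so CDR-SB uses the whole two-sided 0.05.

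**Step 2: error across the two families with no link.** Assume no effect at either dose on any endpoint. The low dose is reached only after the high dose succeeds on the same endpoint, and ADAS-Cog 13 and ADCS-ADL-MCI only after MMSE succeeds. A first false rejection can therefore come only from high-dose CDR-SB or high-dose MMSE:

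P(any) = P(|Z_CDR-SB| > 1.96 or |Z_MMSE| > 1.96) = 0.05 + 0.05 − P(both).

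With rho = 0, P(both) = 0.05² = 0.0025, which gives 0.0975. Other values come from the bivariate normal distribution. The third column counts only rejections in favour of aducanumab, against 0.025 for one test.

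| Assumed rho | Any two-sided rejection | Benefit only |
|---|---|---|
| 0 | 0.0975 | 0.0494 |
| 0.3 | 0.0951 | 0.0476 |
| 0.5 | 0.0907 | 0.0454 |
| 0.7 | 0.0835 | 0.0417 |
| 0.8 | 0.0781 | 0.0390 |
| 0.9 | 0.0704 | 0.0352 |

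A simulation of the full sequence (four endpoints, two doses, 1,000,000 null trials) gave 0.0974, 0.0952, 0.0905, 0.0835 and 0.0783 for rho 0, 0.3, 0.5, 0.7 and 0.8.

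**Step 3: how often the gap is used.** At rho 0.5, P(both) = 0.10 − 0.0907 = 0.0093. The chance that MMSE rejects while CDR-SB does not is 0.05 − 0.0093 = 0.0407. Given a failed high-dose CDR-SB, that is 0.0407 / 0.95 = 4.3%. The corresponding figures are 5.0% at rho 0 and 3.0% at rho 0.8.

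**Step 4: would a dose-by-dose gate be enough?** Suppose the secondary endpoints for a dose open only after CDR-SB succeeds for that dose, all at 0.05. With no effect anywhere, the simulated error is 0.050. Now let the high-dose CDR-SB effect be real and large, and nothing else. Low-dose CDR-SB and high-dose MMSE are then both true nulls and both open at 0.05. Their statistics correlate at 0.5 × rho, so the Step 2 formula gives 0.0975 (rho 0), 0.096 (rho 0.5, correlation 0.25) and 0.092 (rho 0.9, correlation 0.45). Simulation gave 0.098 and 0.096 for rho 0 and 0.5. This gate leaves about 9% to 10%.

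**The case against.** The strongest reply is that the gap is an omission which an SAP would normally close, and the SAP is not shown. An SAP may indeed add the link. However, Section 16.2.2.3 gives an order, a threshold and a stopping rule as if complete, and defers none of this. Version 6.0 does defer the futility criteria, the superiority analysis and the extension-period analyses to the SAP (Sections 16.7.1, 16.7.2 and 16.2.2.6.2). The stated rule gives the wrong result when followed.

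A second reply is that the ranking is tied to Section 6 as a whole, which opens with the primary endpoint, so a secondary endpoint could be taken to rank below CDR-SB. That reading is possible but not compelled: the sentence ranks secondary endpoints only. The rule on comparisons after p > 0.05 sits in the primary paragraph, directly after the dose order, and closes the low dose. The comparison with the primary procedure describes the form of the secondary one and does not make it depend on the primary result.

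The objections to the size carry weight. A reader might infer that the plan promises 5% study-wide and delivers 9%. The documents do not support that: they claim control within each family and print no combined rate. The 9% needs an assumed correlation of 0.5 and the complete null, and it counts rejections in either direction. Nor are all three secondary endpoints independently open: under the complete null the whole excess comes from high-dose MMSE.

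**Conclusion.** The point stands as a rule wrongly fixed in the text: nothing in the protocol stops formal secondary testing after CDR-SB fails. Read literally, the chance of at least one two-sided false rejection across primary and secondary endpoints is about 7% to 10% under the complete null, for assumed correlations of 0.9 to 0. False claims of benefit run at about 3.5% to 4.9% against 2.5%. The comparison with one family at 0.05 is the usual standard for confirmatory claims and not a figure the protocol states.

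A reader might also infer that the primary analysis is compromised. It is not: the CDR-SB test, its alpha and the sample size are unaffected. The consequence arises only if CDR-SB fails and a secondary result is then presented as confirmatory. The text should be corrected before unblinding.

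**What to change.** State in Section 16.2.2.3 that no secondary endpoint is formally tested unless CDR-SB is significant, and place all comparisons in one prespecified chain, each tested at two-sided 0.05:

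1. CDR-SB high dose, then CDR-SB low dose.
2. MMSE high dose, then low dose.
3. ADAS-Cog 13 high dose, then low dose.
4. ADCS-ADL-MCI high dose, then low dose.

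All p-values after the first non-significant test are nominal. A fixed sequence of this kind holds 5% in every configuration of true and null effects.

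If separate chains for each dose are preferred, split alpha between them; Step 4 shows why gating each dose at the full 0.05 will not do. The SAP should carry the same wording.

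The change needs no further patients or data. Formal secondary claims after a failed primary are lost. With the single chain, high-dose secondary claims are also lost if low-dose CDR-SB fails. An equal split avoids that second loss but tests high-dose CDR-SB at 0.025. On the planning assumptions, power there falls from 0.905 to Φ(3.268 − 2.241) = 0.848 with 450 per arm.

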### **9.2. Randomization and Registration of Subjects**

Subjects will be registered at the Screening Visit and randomized only after all baseline assessments have been completed and the Investigator has verified that the subjects are eligible per criteria in Sections 8.1 and 8.2. No subject may begin treatment prior to assignment of a unique identification number (registration) and randomization. Any subject identification numbers or randomization schedule assignments that are assigned will not be reused even if the subject does not receive treatment. Rescreened subjects will be assigned a new number.

Subjects will be randomized to receive aducanumab low dose:aducanumab high dose:placebo in a 1:1:1 ratio. The randomization will be stratified by site and ApoE  $\epsilon$ 4 status (carrier or non-carrier). Subjects randomized to placebo at the start of the placebo-controlled period will also be randomized to receive dose-blinded aducanumab (low dose:high dose, 1:1 ratio) for the LTE period and randomization will be stratified by subject ApoE  $\epsilon$ 4 carrier status. Treatment group assignments for the placebo-controlled period and the LTE period will be assigned at Study Day 1. Enrollment will be monitored, via the IRT, such that the population of subjects with mild AD represents a small percentage of the total enrolled in the trial. Subjects who withdraw from the study may not be replaced.

Refer to the Study Reference Guide for details on registration and randomization.

CONFIDENTIAL

The information contained herein may not be used, disclosed, or published without the written consent of Biogen MA Inc.

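### The dose-by-dose gating in Section 16.2.2.3 does not control Type I error across the secondary endpoints as claimed: maximum familywise error about 9.1% to 9.75%

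*Protocol*

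**What the plan says.** Section 16.2.2.3 orders the dose comparisons on the primary endpoint as "aducanumab high-dose versus placebo and aducanumab low-dose versus placebo", each judged at 0.05. For the secondary endpoints, ranked MMSE, ADAS-Cog 13, ADCS-ADL-MCI, it states: "In order to control for a Type I error for the secondary endpoints, a sequential closed testing procedure will be used". Two rules implement this.

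- Within an endpoint: "for each of the secondary endpoints, a sequential (closed) testing procedure, as for the primary endpoint, will be used". The low dose is tested only if the high dose has succeeded on that endpoint.
- Between endpoints: if one or both comparisons fail, "all endpoint(s) of a lower rank will not be considered statistically significant for 1 or 2, respectively". One failure closes the lower ranks for that comparison; two failures close them for both.

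Section 16.2.2.1 adds: "All statistical tests will be 2-sided". No division of alpha between the doses is mentioned.

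**The concern.** A fixed sequence protects familywise error because there is only one path, and the first true null on it is tested at 0.05. Here the path forks. Suppose the high dose succeeds on MMSE. Low-dose MMSE and high-dose ADAS-Cog 13 are then both open at 0.05, and failing one does not close the other. The same fork recurs at the next rank. A closed test would need a level-0.05 test of the intersection of those two hypotheses; rejecting when either p-value is below 0.05 is not such a test.

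At stake is the protocol's statement that the set of secondary claims over both doses is protected at 5%. A working high dose with a weaker low dose is an outcome that opens the fork, and Section 5.3 itself describes a dose-dependent slowing of decline in the earlier study.

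**Working it through.** **Inputs.** Alpha: Section 16.8 gives "a final significance level of 0.05", two-sided, so the critical value is 1.96. Allocation (Section 9.2): "Subjects will be randomized to receive aducanumab low dose:aducanumab high dose:placebo in a 1:1:1 ratio". Planning effect (Section 16.8): "a true mean difference of 0.5 in change from baseline CDR-SB at Week 78", with SD 1.92, 30% dropout, about 90% power and 450 per arm, later raised to 535. Correlation between endpoints, ρ: not in the protocol; taken from 0 to 1.

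**The plan's own figure.** Evaluable per arm: 2 × 1.92² × (1.96 + 1.2816)² / 0.5² ≈ 310. Dividing by 0.70 gives 443, against 450 planned. With 450 × 0.70 = 315 evaluable, power is 0.905. The stated 90% reproduces. The protocol prints no familywise error figure, only the claim of control.

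**Which tests can be open together.** Let the high dose's first true null be at rank a and the low dose's at rank b.
- If b is at or below a in the ranking, the low-dose test at b can be reached only after the high dose has been falsely rejected at a, so the error is at most 0.05.
- If b is above a, two true nulls can be open together, each at 0.05. Later nulls are reached only through one of these.

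The maximum is therefore the probability that at least one of two level-0.05 tests rejects.

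**Correlation of the two tests.** With equal arms, the two dose contrasts on one endpoint share the placebo mean. Their covariance is σ²/n and each variance is 2σ²/n, so they correlate 0.5. Low dose on one endpoint and high dose on the next correlate 0.5ρ.

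**Maximum error** = P(|Z1| > 1.96 or |Z2| > 1.96), bivariate normal with correlation 0.5ρ:

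| ρ | 0.5ρ | Error |
|---|---|---|
| 0 | 0 | 1 − 0.95² = 0.0975 |
| 0.3 | 0.15 | 0.0969 |
| 0.5 | 0.25 | 0.0959 |
| 0.7 | 0.35 | 0.0943 |
| 1 | 0.5 | 0.0907 |

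**Simulation of the full rule** (four endpoints by two doses, CDR-SB as the first rank). Real effects: both doses on CDR-SB and the high dose on MMSE; everything else null. All errors counted here are in the secondary family.

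| Setting | ρ = 0.3 | ρ = 0.5 | ρ = 0.7 |
|---|---|---|---|
| Real effects near-certain to be detected | 0.097 | 0.096 | 0.094 |
| 90% power at each real effect (mean of Z = 1.96 + 1.28 = 3.24) | about 0.07 | about 0.063 | about 0.055 |
| Single list, stop at first failure (effects near-certain) | 0.050 | 0.050 | 0.050 |

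Under the global null the overall error is 0.050. The CDR-SB family alone, high then low, is 0.050. In the near-certain setting, the false rejection rate is 0.050 for low-dose MMSE and 0.050 for high-dose ADAS-Cog 13 taken separately.

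The simulation assumes that CDR-SB gates the secondary endpoints dose by dose, in the same way as the ranks below it. The near-certain row does not depend on this, because both CDR-SB effects are real there.

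**The case against.** Much of the opposing case stands.

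- The trial's main conclusion is untouched. High then low dose on CDR-SB is a proper fixed sequence and holds 0.05.
- A reader might infer that familywise error is simply about 9.5%. That is a ceiling, reached under a partial null with near-certain success at each gate. At the protocol's own 90% power the excess is smaller, and under the global null there is none.
- A reader might pool low-dose CDR-SB with high-dose MMSE and call that a breach. That pooled error does reach 0.094 to 0.097 at ρ of 0.7 to 0.3, but the section makes separate claims for the primary and the secondary endpoints and never promises 5% across the two. The claim that fails is the one for the secondary endpoints.
- A reader might infer that any one secondary or low-dose claim carries nearly double its stated error. It does not; each hypothesis is tested at 0.05. What rises is the chance of at least one false claim.
- The rule is not two independent dose chains, since the high dose gates the low dose on every endpoint. One gate is missing: from low dose at a rank to high dose at the next.

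Two further defences are weaker. The statistical analysis plan may specify something else, but this section fixes a rule and asserts what it achieves, whereas Section 16.7.1 expressly defers the futility criteria. The sponsor may also have meant that any failure stops everything; the closing distinction between one and two failed comparisons would then have no purpose, and the sentence would still need rewriting.

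**Conclusion.** The rule as written does not control familywise error in the strong sense for the secondary endpoints, contrary to the protocol's statement. The maximum within that family is about 9.1% to 9.75%, for example 0.094 to 0.097 at between-endpoint correlations of 0.7 to 0.3. With 90% power at each real effect and the same correlations it is about 0.055 to 0.07. These figures rest on the dose-specific reading of the last sentence, on equal arms sharing one placebo group, and on assumed between-endpoint correlations. The ceiling exceeds 9% at every correlation from 0 to 1, so the conclusion does not depend on that assumption. The defect concerns secondary claims taken as a set; it does not weaken the CDR-SB result for either dose.

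**What to change.** Before unblinding, replace the last sentence of Section 16.2.2.3 with one of these.

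1. A graphical procedure that, after a high-dose success at a rank, splits alpha between the low dose at that rank and the high dose at the next, and recycles what is won, with weights fixed in advance. This keeps the evident intent that the high dose may continue after a low-dose failure. Cost: less alpha on each branch.
2. One ordered list: high then low dose on CDR-SB, then MMSE, ADAS-Cog 13 and ADCS-ADL-MCI, stopping all later tests at the first failure. Cost: a low-dose failure ends every later high-dose secondary test.

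Either is a change of wording in the protocol and the analysis plan, with no effect on sample size or conduct. If the sponsor prefers the present rule, it should withdraw the claim of Type I error control across the secondary endpoints and both doses.
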